6.2.3 Dose fractionation and specification

The prescription dose per fraction to the PTV will be 8 Gy per fraction for a bone or lung index lesion and 6Gy per fraction for any liver or subcutaneous index lesion.

The total dose for dose level 1 (our starting dose level) will be one will be 24Gy over 3 fractions for a bone or lung index lesion and 18Gy over three fractions for any liver or subcutaneous index lesion.

If we encounter a dose limiting toxicity, we will then reduce our total dose to dose level -1. The total dose for dose level -1 will be 16Gy over 2 fractions for a bone or lung index lesion and 12Gy over two fractions for any liver or subcutaneous index lesion.

Dose rate: For the purpose of this study, dose rate utilized will be that which is commissioned by the manufacturer and the medical physics group for external beam radiotherapy delivery by the University of Washington Department of Radiation Oncology. There will be no special dose rate modifications required for this study.

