6.3 Ipilimumab Administration

Ipilimumab will be given in the outpatient setting. Patients will receive ipilimumab at 3 mg/kg i.v. delivered as per the package insert every 3 weeks (+/- 2 days) for treatments. Patients will be monitored in the clinic after the infusion and discharged when deemed stable by the clinical staff. Medications to treat hypersensitivity reactions should be immediately available, and may include epinephrine, diphenhydramine, methylprednisolone and nebulized albuterol.

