8.4.1 Escalation Design

CONFIDENTIAL

This material is the property of the study sponsor. Do not disclose or use except as authorized in writing by the study sponsor

Printed on 1/31/2017

Because of the successful outcome with 2 and 3 fractions of SBRT in the University of Pennsylvania Phase 1 trial, the initial dose level in this study will be Dose level 1 (3 fractions of SBRT).

Dose level 1. This trial will begin enrolling at dose level 1, 3 fractions of SBRT, which has been shown to be safe in the Phase 1 trial at University of Pennsylvania. However, if one DLT has been observed in any patient, then all remaining patients must be followed for 30 days after the 4th or final injection. Two or more DLTs will cause de-escalation to Dose level -1, which will be the MTD.

Dose level -1. If two or more DLTs are observed in Dose Level 1, then all subsequent patients will be treated at Dose Level -1. If DLTs are observed at dose level -1, this will cause termination of the study.

Replacement of patients: Subjects/patients who discontinue from the study for reasons unrelated to the study (e.g. personal reasons or adverse events after registration but prior to receiving study therapy) may be replaced as required for the study to meet its objectives. Patients that have received study therapy, but who withdraw for reasons unrelated to toxicity prior to the required observation period to determine absence of DLT, will not count toward dose escalation rules and may be replaced as required. The decision to remove a subject/patient and to replace dropouts will be made by the principal investigator. The replacement will receive the same treatment or treatment sequence (as appropriate) as the allocation number replaced.

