Immunologic Endpoints: For measures of lymphocyte activation, outcomes will first be described using plots and descriptive statistics. Natural log transformation may be applied, as necessary, prior to statistical comparison. Within-patient differences (e.g., baseline vs. post-treatment) will be examined by Student's t test for paired data or nonparametric Wilcoxon signed ranks test. For lymphocyte analyses, outcomes will first be described using plots and descriptive statistics. For T cell response, the number of immune responses (>2 fold pre/post increase) will be tabled by fraction dose level. The overall immune response rate and 95% exact CI will be estimated separately for previously untreated and previously treated metastatic patients treated at the MTD.

With several post-treatment samples intended, trends over time may be investigated by repeated measures ANOVA (if data are complete). Alternatively, mixed effects models will describe trends in individual APC and T cell outcomes measured during immunotherapy, including drug doses as fixed effects. Although the number of subjects is modest, serial blood measures for immune monitoring are intended. (Thus, longitudinal modeling may be successful. We will attempt to extend this investigation to longitudinal methods for multivariate data with the goal of modeling jointly the inter-dependency among several longitudinal outcomes. For example, a joint analysis may determine how the association between the induction of CD86 on APCs and antigen-specific T cells evolves over time. Because the number of immunologic outcomes to be modeled jointly will be small (several at most), we will attempt to use the pairwise model fitting approach for maximum likelihood estimation as previously described.(27)

CONFIDENTIAL

This material is the property of the study sponsor. Do not disclose or use except as authorized in writing by the study sponsor

Printed on 1/31/2017

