8.6 Sample Size/Power

If the Phase II study investigates both SBRT fraction dose levels for both strata, then a total of 40 patients will be enrolled on the study. There will be 40 patients enrolled at the Phase II dose. An objective response rate of 10.9% (by modified WHO criteria) was observed by Hodi et. al. in 137 previously treated metastatic melanoma patients treated with ipilimumab alone.(3) We anticipate that the combination of SBRT and ipilimumab will result greater efficacy for each stratum. If the true immune-related response rate is 20%, then the probability of observing no responses in 14 patients in either stratum, is <0.05.

With regard to statistical power, our preliminary clinical data on 16 patients treated on the single-infusion CD40 mAb trial indicate the mean difference \pm SD_{diff} between post- and pre-treatment percentages of CD19+ B cells expressing CD86 were: 17.1% \pm 11.1%, with effect size of 1.5 SD_{diff} units. By pooling over strata at the MTD, with a total of 28 patients enrolled, there is >80% power to detect a more modest effect size of $\frac{3}{4}$ SD_{diff} units, based on a paired t-test at 2-sided alpha level of 0.005 after adjusting for testing of multiple APC measures. Moreover, at the end of our current Phase I study of anti-CTLA-4 antibody (tremelimumab) and anti-CD40 antibody (CP-870,893) (UPCC 05609), we will evaluate pre/post differences in percentages of CD19+ B cells expressing CD86 and other relevant immune outcomes and we will update the power calculation for those effect sizes.

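### The immune analyses make no use of the site stratum and the mixed model's dose term is undefined; a stratified pre/post test and a by-stratum table would cost almost nothing

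*Combined protocol and SAP*

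**What the plan says.** **Strata.** Section 8.1 plans 20 patients in each of two index-lesion strata, enrolled independently. Section 6.2.3 ties the SBRT dose to the stratum: "8 Gy per fraction for a bone or lung index lesion and 6Gy per fraction for any liver or subcutaneous index lesion", which at dose level 1 totals "24Gy over 3 fractions for a bone or lung index lesion and 18Gy over three fractions for any liver or subcutaneous index lesion".

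**Clinical outcomes.** Section 8.5 tables toxicity and clinical response by stratum and SBRT fraction dose level.

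**Immune outcomes.** For T-cell response, section 8.5 says "the number of immune responses (>2 fold pre/post increase) will be tabled by fraction dose level". Immune response rates with exact intervals are then split by prior treatment, not by site. Pre/post changes are examined by a paired t test or the signed ranks test. For repeated samples, "mixed effects models will describe trends in individual APC and T cell outcomes measured during immunotherapy, including drug doses as fixed effects". Section 8.6 powers the paired test "By pooling over strata at the MTD" with 28 patients, an effect of 0.75 SD of the differences and a two-sided alpha of 0.005, and states power above 80%.

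**Ipilimumab.** One level is planned: "Patients will receive ipilimumab at 3 mg/kg i.v. delivered as per the package insert every 3 weeks" (section 6.3). The number of infusions can vary, since section 8.4.1 refers to follow-up after the "then all remaining patients must be followed for 30 days after the 4th or final injection".

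**The concern.** The stratum is the one factor that the design fixes in advance, and it carries two differences at once: site and SBRT dose. Immune pharmacodynamic change is a secondary objective, and the trial's rationale is that SBRT primes the response. A reader would therefore expect immune results to be laid out by stratum, as toxicity and clinical response are. They are not.

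Three things follow. The T-cell table can collapse to a single row. The pooled pre/post test may use a standard error that is larger than it should be. And two analysts could fit different longitudinal models from the same sentence, because the dose term has at least three meanings.

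**Working it through.** **1. The plan's own power.** Inputs from section 8.6: n = 28, effect 0.75 SD of the differences, two-sided alpha 0.005. Noncentral t with 27 df and noncentrality 0.75 × √28 = 3.97 gives power 0.808, so the statement reproduces. At the planned 40 patients it is 0.955.

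**2. Cost of a stratum term.** Testing the average of the two stratum means with the within-stratum variance uses n − 2 df. If the strata do not differ, power goes from 0.808 to 0.804 at n = 28 and from 0.955 to 0.954 at n = 40.

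**3. Cost of leaving it out.** The strata have fixed, equal sizes, so the sampling variance of the overall mean change contains only within-stratum variance. The pooled SD also contains the gap between the strata. If mean change differs by δ within-stratum SDs, then

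pooled SD ÷ within-stratum SD = √(1 + (δ²/4) × n/(n − 1)).

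At n = 28:
- δ = 0.5: √(1 + 0.0625 × 28/27) = 1.032
- δ = 1.0: √(1 + 0.25 × 28/27) = 1.122

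The standard error is too wide by those factors. Now take 0.75 in within-stratum SDs. The documents give no δ, so these values are assumptions.

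| n | δ | Power, pooled | Power, stratified |
|---|---|---|---|
| 28 | 0.5 | 0.78 | 0.80 |
| 28 | 1.0 | 0.68–0.70 | 0.80 |
| 40 | 0.5 | 0.94 | 0.95 |
| 40 | 1.0 | 0.89–0.91 | 0.95 |

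Where a range is shown, the lower figure puts the inflated SD into the noncentral t. The higher one comes from simulating the pooled test with fixed strata, which is the more exact of the two. In the same simulation with no average change, a 1-SD stratum difference reduces a nominal 5% error rate to about 3%, while the stratified test holds its level.

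**4. The T-cell table.** If both strata stay at dose level 1, fraction dose level takes one value. The table then has one row, which merges 24 Gy bone or lung patients with 18 Gy liver or subcutaneous patients.

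**5. The dose term, reading by reading** (rank of the fixed-effects design):
- *mg/kg level*: the same for everyone. Intercept, time and dose have rank 2 of 3, so the term is not estimable.
- *Infusion number or cumulative infusions*: rank 3 of 3 if the baseline and post-SBRT samples (section 6.5) are included, so it is estimable. On ipilimumab-period samples alone, on the planned schedule, it is aliased with linear time (rank 2 of 3), but it can itself be the time axis (rank 2 of 2).
- *SBRT dose*: estimable alone (rank 3 of 3). At a common fraction level it equals the stratum (rank 3 of 4 with both), so site and dose cannot be separated.

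**The case against.** The case on the other side is substantial.

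- **The model can be fitted.** A reader might infer from the single ipilimumab level that the mixed model fails as written. That holds only for the mg/kg reading. The phrase is plural and follows a reference to measurements during immunotherapy, so infusion count is at least as natural, and it works. This objection stands: the fault is an undefined term.
- **Stratum level differences do not go into error.** A constant difference in level cancels in a paired difference. In a random-intercept simulation (28 patients, 5 times, 1-SD level difference), leaving stratum out did not change the residual variance (0.98 in both fits) or the slope standard error (0.059 in both). It only raised the between-patient variance (0.97 to 1.24). Only a difference in *change* matters.
- **The stated power is not wrong.** A reader might infer that any stratum difference takes power below the stated 80%. Section 8.6 defines the effect in SDs of the differences actually tested, so 0.808 already includes whatever contributes to that SD. The loss appears only when 0.75 is read in within-stratum SDs. Even then power at 40 patients is 0.89 or more for differences up to 1 SD. At 1.5 SD one stratum would have a mean change of 0.75 − 0.75 = 0, which is not a planning value.
- **Pooling is limited and declared.** It is stated only for the paired test. The mixed model is silent on strata, and the response-rate intervals are split by prior treatment.
- **The stakes are modest.** These are secondary, largely exploratory analyses with no decision rule attached, and the assays depend on available cells or serum.

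None of this explains why stratum is used for toxicity and clinical response tables but not for immune ones, or gives a reason to prefer the unstratified test when the stratified one is nearly free.

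**Conclusion.** This is a cheap improvement, not an error that invalidates the analysis. No immune analysis is specified to use the stratum, and the longitudinal dose term needs a definition. The size of the gain depends on an unknown: with no stratum difference in mean change nothing is gained and about 0.004 of power is lost at n = 28. With an assumed 1-SD difference the stratified test recovers about 0.10 to 0.12 of power at n = 28 (0.804 against 0.70 or 0.68) and about 0.04 to 0.07 at n = 40 (0.954 against 0.91 or 0.887). These figures assume equal strata, a common within-stratum SD, and the 0.75 effect in within-stratum SDs. The one-row table and the undefined term do not depend on any of these assumptions.

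**What to change.** In section 8.5:

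1. Table immune responses by stratum and SBRT fraction dose level, as is done for clinical response.
2. Base the parametric pooled pre/post test on the average of the two stratum means, with the within-stratum variance. This does not cover the signed ranks alternative, which would need its own stratified form if it is used.
3. Replace the dose term with fixed effects for visit (infusion number), stratum and visit-by-stratum, plus a random patient effect. Add SBRT fraction level only if a stratum de-escalates. State that SBRT dose and site cannot be separated at a common fraction level.

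The cost is wording and one degree of freedom in the pooled test. No new data are needed. The interaction adds parameters with only 20 patients per stratum, so its estimates should be presented as descriptive.

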8.6 Sample Size/Power

If the Phase II study investigates both SBRT fraction dose levels for both strata, then a total of 40 patients will be enrolled on the study. There will be 40 patients enrolled at the Phase II dose. An objective response rate of 10.9% (by modified WHO criteria) was observed by Hodi et. al. in 137 previously treated metastatic melanoma patients treated with ipilimumab alone.(3) We anticipate that the combination of SBRT and ipilimumab will result greater efficacy for each stratum. If the true immune-related response rate is 20%, then the probability of observing no responses in 14 patients in either stratum, is <0.05.

With regard to statistical power, our preliminary clinical data on 16 patients treated on the single-infusion CD40 mAb trial indicate the mean difference \pm SD_{diff} between post- and pre-treatment percentages of CD19+ B cells expressing CD86 were: 17.1% \pm 11.1%, with effect size of 1.5 SD_{diff} units. By pooling over strata at the MTD, with a total of 28 patients enrolled, there is >80% power to detect a more modest effect size of $\frac{3}{4}$ SD_{diff} units, based on a paired t-test at 2-sided alpha level of 0.005 after adjusting for testing of multiple APC measures. Moreover, at the end of our current Phase I study of anti-CTLA-4 antibody (tremelimumab) and anti-CD40 antibody (CP-870,893) (UPCC 05609), we will evaluate pre/post differences in percentages of CD19+ B cells expressing CD86 and other relevant immune outcomes and we will update the power calculation for those effect sizes.

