Statistical Methodology	This is a stratified phase II study of escalating fractions of stereotactic body radiotherapy (SBRT) combined with immunotherapy for previously untreated or previously treated metastatic melanoma patients. Phase I was stratified by site: bone or lung vs. liver or s.c. Six patients were enrolled per dose cohort. Phase II is stratified by site: bone or lung vs. liver or s.c. In phase II, 20 patients will be treated at the MTD in each stratum. Descriptive statistics will be generated for both phases of the study.

CONFIDENTIAL

This material is the property of the sponsor. Do not disclose or use except as authorized in writing by the study sponsor

Printed on 1/31/2017

1 Introduction

This document is a protocol for a human research study. This study is to be conducted according to US and international standards of Good Clinical Practice (FDA Title 21 part 312 and International Conference on Harmonization guidelines), applicable government regulations and Institutional research policies and procedures.

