3.1 General Design

This is a stratified phase II study of escalating fractions of stereotactic body radiotherapy (SBRT) combined with immunotherapy for previously untreated or previously treated metastatic melanoma patients. Patients will undergo a short course of high dose SBRT to a single index lesion that measures 1 cm to 5 cm. These fractions will be administered several days apart. Radiotherapy will be immediately followed by ipilimumab, at the FDA-approved dose and schedule.

RADVAX TRIAL

Study Duration: The expected accrual rate = 15 pts/yr. The protocol is designed for a maximum total of 40 patients. The expected total study duration is 3 to 3 ½ yrs needed to complete both phases, allowing for suspensions for interim analyses.

*Study Enrollment is intended to mean consultation

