8.1 Design

This is a stratified Phase II study of escalating fractions of stereotactic body *radiotherapy* (SBRT) combined with immunotherapy for previously untreated or previously treated metastatic melanoma patients. Patients will undergo a short course of high dose SBRT to a single index lesion that is suitable for SBRT. These fractions will be administered several days apart. Radiotherapy will be immediately followed by ipilimumab, at the FDA-approved dose and schedule.

Stratified Phase II study: With safety data from an identical University of Pennsylvania study, SBRT fractions of two and three fractions has been shown to be safe. At UW/SCCA the Phase II study begins with Dose Level 1. If three fractions of SBRT are found to not be safe, the dose level will be reduced to Dose level -1 for the phase II portion of that stratum.

Stratification by Site of Index Lesion						
Dose Level	Stratum 1: bone or lung			Stratum 2: liver or subcutaneous		
	Dose per fraction	Fractions	# Patients	Dose per fraction	Fractions	# Patients
-1	8 Gy	2	6	6 Gy	2	6
1	8 Gy	3	6	6 Gy	3	6

The MTD has been defined by the Phase I trial at the University of Pennsylvania as 3 fractions of SBRT. The Phase II study can commence at UW/SCCA at dose level 1 (above). Patients will be treated at the MTD defined for their index lesion site. In Phase II, patients will be stratified by disease site: Stratum 1: phase 1 bone or lung and Stratum 2: phase 1 liver or subcutaneous. Stratum-specific response rates will be calculated. Enrollment will proceed independently for the

CONFIDENTIAL

This material is the property of the study sponsor. Do not disclose or use except as authorized in writing by the study sponsor

Printed on 1/31/2017

two strata. Forty total patients will be enrolled in this phase. Thus a maximum of 40 patients will be entered at the MTD. Twenty patients will be enrolled in each stratum

8.2 Objectives:

Phase II study: The primary objectives are to determine for each stratum, immune-related clinical response rate, immune-related progression-free survival rate at 6 months (irPFS6), and overall survival rate at 12 months (OS12). The secondary objectives are to gather additional data on acute and late toxicity and immune pharmacodynamic changes.

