8.3 Endpoints

Toxicity: CTCAE version 4.0 grades will be employed. Any patient who receives any amount of radiotherapy or study medication will be included in the toxicity analysis.

Dose-limiting toxicity (DLT) is defined generally as associated with the treatment, and for ipilimumab, that the event must be consistent with an immune-related effect. DLT is experienced during study treatment or within 30 days after last injection of ipilimumab, as long as the patient has not started another systemic treatment for cancer and is defined more precisely in Section 5.2.

Maximum tolerated SBRT fraction (MTD) is defined as the SBRT fraction dose level at which 0-1/6 patients experience DLT and at least 2 patients treated at the next higher dose level experience DLT (or the apparent MTD is Dose level 1).

Late toxicity is defined generally as an adverse event associated with the treatment which occurs beyond 30 days after last injection (i.e., adverse events which are observed months after treatment are most likely associated with SBRT) and is defined more precisely in Section 5.2.

Response: Immune-related clinical response will be scored on a non-index lesion using immune-related response criteria (irRC) according to irRECIST 1.1 (48). Patients who do not complete a clinical response evaluation, with the exception of those patients with rapidly progressing disease, will be scored as unevaluable. The immune-related clinical response rate is defined as the proportion of patients treated at the MTD who achieve either a complete or partial immune-related response. Unevaluable patients are included in denominator for the calculation of the objective response rate.

Immunologic outcomes include: 1) analysis of lymphocyte subsets and lymphocyte activation, 2) analysis of antigen-specific T cells and 3) tumor-specific T cells, as described in Section 7.2.2. For T cell response analyses, overall immune response is defined as >2 fold pre-treatment/post-treatment increase in any of the key T cell parameters.

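### Section 8.6 promises 40 patients at the Phase II dose even if both dose levels are used under a 40-patient cap; a stratum that de-escalates cannot reach 20 at the MTD

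*Combined protocol and SAP*

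**What the plan says.** Section 8.6 takes the case in which both dose levels come into use in each stratum, and for that case it says: "then a total of 40 patients will be enrolled on the study. There will be 40 patients enrolled at the Phase II dose". The Study Summary (Statistical Methodology) says "In phase II, 20 patients will be treated at the MTD in each stratum".

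Section 3.1 sets the limit: "The protocol is designed for a maximum total of 40 patients". Section 8.1 repeats it as a ceiling, "Thus a maximum of 40 patients will be entered at the MTD", and fixes the starting point: "At UW/SCCA the Phase II study begins with Dose Level 1".

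The de-escalation trigger is given in two ways. Section 8.4 (and Section 6.2.3) moves later patients to level -1 after one DLT. Section 8.4.1 requires two or more and says that level -1 then becomes the MTD.

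Section 8.3 defines the response rate as "the proportion of patients treated at the MTD who achieve either a complete or partial immune-related response". Section 8.5 likewise limits irPFS and OS to patients treated at the MTD. The exact-CI table in Section 8.5 assumes 14 patients per stratum. In Section 8.6 the zero-response statement also uses 14, and the immune power statement uses 28 pooled over strata.

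**The concern.** A patient treated at level 1 before a de-escalation uses one of the 40 places but is not at the MTD once level -1 takes that role. The Section 8.6 sentences are written for exactly the case in which this happens, yet they put the whole study at the Phase II dose. The Study Summary makes the same promise per stratum without any condition.

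Section 8.2 names response rate, irPFS at 6 months and OS at 12 months as the primary Phase II objectives, and all three are estimated at the MTD. In a de-escalated stratum their sample size is therefore below the stated 20. The plan does not say by how much, or whether the printed precision and power allow for it.

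**Working it through.** **Inputs from the plan.** Cap 40, planned as 20 per stratum (Sections 3.1 and 8.1); start at level 1 (8.1); trigger of one DLT (8.4) or two or more (8.4.1); cohort of 6 per dose level and stratum (8.1 table; the MTD definition in 8.3 also uses 6); 14 per stratum and 28 pooled (8.5, 8.6). The replacement rule in 8.4.1 covers patients who leave before therapy or withdraw for reasons unrelated to toxicity. It does not refill level 1 places.

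**Step 1: the plan's own figures reproduce.**
- Exact 95% CI for 2/14: 1.8–42.8%, as printed. The other two-sided rows also match.
- 14/14, one-sided lower bound: 0.05^(1/14) = 80.7%, as printed.
- Zero responses at a true rate of 20%: 0.8^14 = 0.044, below 0.05 as stated.
- Paired t-test, effect 0.75 SD, two-sided alpha 0.005, n = 28 (noncentral t, 27 df, noncentrality 0.75√28): power 0.808, above 80% as stated.
- Operating characteristics in 8.4.2: P(at most 1 DLT in 6), e.g. 0.233 at a 40% DLT rate, printed as 0.23.

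**Step 2: the promised 40 does not reproduce.** With k patients treated at level 1 in a de-escalated stratum, the number at level -1 is at most 20 − k.

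| Situation | k | At MTD, that stratum | At MTD, both strata de-escalated | Total needed to keep 20 + 20 at level -1 |
|---|---|---|---|---|
| One-DLT trigger, earliest case | 1 | 19 | 38 | 42 |
| Two-DLT trigger, earliest case | 2 | 18 | 36 | 44 |
| Full cohort of 6 | 6 | 14 | 28 | 52 |

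Every total in the last column exceeds the cap of 40.

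**Step 3: when the printed statements fail.** 20 − 6 = 14 and 40 − 12 = 28, so they hold while k is 6 or less in each stratum. Beyond that:
- Zero responses: 0.8^13 = 0.055, no longer below 0.05.
- Pooled power: 0.786 at n = 27 and 0.709 at n = 24, no longer above 80%.

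**Step 4: how likely, and how many remain.** The documents give no expected DLT rate; 10% and 20% are assumptions.

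| Two-DLT trigger, per stratum | DLT rate 10% | DLT rate 20% |
|---|---|---|
| P(≥2 DLTs), first 6 patients | 0.11 | 0.34 |
| P(≥2 DLTs), all 20 patients | 0.61 | 0.93 |
| Left for level -1 given de-escalation, first-6 reading | 14–18 | 14–18 |
| Mean left given de-escalation, all-20 reading | 8.4 | 11.2 |

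For the last row, P(second DLT at patient k) = (k − 1)p²(1 − p)^(k−2), and 20 − k is averaged over k = 2 to 20 and divided by P(≥2 in 20). This ignores the delay before a DLT is known, which would put more patients at level 1. Under the one-DLT trigger, the de-escalation probabilities are 0.47 / 0.74 on the first 6 and 0.88 / 0.99 over 20.

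**Step 5: effect on precision near a 20% response rate (exact 95% CI).** 4/20: 5.7–43.7%. 3/14: 4.7–50.8%. 2/10: 2.5–55.6%.

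**The case against.** The strongest reply is that the plan never prints a CI at 20 per stratum. Its precision and power rest on 14 and 28, which may already allow for a cohort of 6 at level 1. A reader might infer that precision is overstated in every stratum that de-escalates. The documents do not support that: with 6 or fewer at level 1, at least 14 remain and the printed table is met or bettered. This part of the objection stands. However, the plan does not say where 14 and 28 come from (20 − 6 and 40 − 12 is an inference), and nothing in 8.4.1 limits the two-DLT trigger to the first six patients.

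A reader might also take 61% and 93% as the chance of de-escalation. Those figures need both the all-20 reading and the assumed DLT rates. The MTD definition in 8.3 and the operating characteristics in 8.4.2 point to a judgement on 6 patients, which gives 11% and 34%. Section 8.4.1 also describes level 1 as already shown safe in the earlier Phase I trial. Only the range can be defended.

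Finally, a reader might infer that level 1 responses disappear. They do not: Section 8.5 tables responses by stratum and dose level, and restricting the rate to the MTD may be deliberate.

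None of this repairs the two sentences in 8.6. The Section 8.1 ceiling of 40 at the MTD is compatible with a smaller number, but the flat promises in 8.6 and the Study Summary are not.

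**Conclusion.** The stated sample size is wrong under its own condition, whichever trigger applies. If both strata de-escalate, at most 38 (one-DLT trigger) or 36 (two-DLT trigger) of the 40 can be at the MTD, and 28 after full cohorts of 6. In the mildest case the shortfall is one or two patients per stratum. After a full cohort it is six, and on the all-20 reading of the two-DLT trigger it averages 11.6 or 8.8 (20 − 8.4 and 20 − 11.2).

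The effect on the printed precision and power is conditional: they fail only when more than 6 patients in a stratum (for the pooled power, more than 12 in total) were treated at level 1. On the all-20 reading that is a real possibility: given de-escalation, the second DLT falls after patient 6 in 81% of cases at an assumed 10% DLT rate and 63% at 20%. If neither stratum de-escalates, 20 per stratum is feasible and there is no conflict.

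**What to change.** - Replace the two sentences in 8.6 and align the Study Summary, 8.1 and 8.5. State 20 per stratum at the MTD only if there is no de-escalation; otherwise at most 20 minus the number already treated at level 1, under the cap of 40. It is an upper bound because 8.4.1 ends the study if DLTs occur at level -1.
- Say which scenario the 14 and 28 describe.
- Print exact CIs for n = 20, n = 14 and a smaller n.
- Restate the below-0.05 and above-80% claims as conditional on at least 14 per stratum and at least 28 pooled at the MTD.
- Reconcile the triggers in 8.4 and 8.4.1, and say over how many patients DLTs are counted. This review does not say which trigger is right.
- Optionally, show the all-treated response rate beside the MTD-only rate in a de-escalated stratum.

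The cost is wording and a few table rows. The stated size and precision become less favourable.
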